8.3.8 Photograph of Rash

Photographs of the rash are highly recommended to be taken immediately, along with any additional information that may assist the investigator to evaluate the skin reaction, skin eruption or rash occurrence in determining etiology and drug relationship.

8.4 Adverse Events, Serious Adverse Events, and Other Reportable Safety Events

The definitions of an AE or SAE, as well as the method of recording, evaluating, and assessing causality of AE and SAE and the procedures for completing and transmitting AE, SAE, and other reportable safety event reports can be found in Appendix 3.

Adverse events, SAEs, and other reportable safety events will be reported by the participant (or, when appropriate, by a caregiver, surrogate, or the participant's legally authorized representative).

The investigator and any designees are responsible for detecting, documenting, and reporting events that meet the definition of an AE or SAE as well as other reportable safety events. Investigators need to document if an SAE was associated with a medication error, misuse, or abuse. Investigators remain responsible for following up AEs, SAEs, and other reportable safety events for outcome according to Section 8.4.3.

The investigator, who is a qualified physician, will assess events that meet the definition of an AE or SAE as well as other reportable safety events with respect to seriousness, intensity/toxicity and causality.

8.4.1 Time Period and Frequency for Collecting AE, SAE, and Other Reportable Safety Event Information

AEs, SAEs, and other reportable safety events that occur after the participant provides documented informed consent, but before intervention randomization, must be reported by the investigator under any of the following circumstances:

- if the participant is receiving placebo run-in or other run-in treatment,
- if the event causes the participant to be excluded from the study,
- if it is the result of a protocol-specified intervention, including, but not limited to washout or discontinuation of usual therapy, diet, placebo, or a procedure.

From the time of intervention randomization through 164 days after cessation of intervention, all AEs, SAEs and other reportable safety events must be reported by the investigator.

Additionally, any SAE brought to the attention of an investigator any time outside the period specified in the previous paragraph also must be reported immediately to the Sponsor if the event is considered related to study intervention.

Investigators are not obligated to actively seek AEs or SAEs or other reportable safety events in former study participants. However, if the investigator learns of any SAE, including a death, at any time after a participant has been discharged from the study, and the investigator considers the event to be reasonably related to the study intervention or study participation, the investigator must promptly notify the Sponsor.

All initial and follow-up AEs, SAEs, and other reportable safety events will be recorded and reported to the Sponsor or designee within the time frames as indicated in [Table 5](#).

Exception: A positive pregnancy test at the time of initial screening is not a reportable event unless the participant has received study intervention.

Table 5 Reporting Time Periods and Time Frames for Adverse Events and Other Reportable Safety Events

Type of Event	Reporting Time Period: Consent to Randomization/Allocation	Reporting Time Period: Randomization/Allocation through Protocol-specified Follow-up Period	Reporting Time Period: After the Protocol-specified Follow-up Period	Time Frame to Report Event and Follow-up Information to Sponsor:
NSAE	Report if: - due to protocol-specified intervention - causes exclusion - participant is receiving placebo run-in or other run-in treatment	Report all	Not required	Per data entry guidelines
SAE	Report if: - due to protocol-specified intervention - causes exclusion - participant is receiving placebo run-in or other run-in treatment	Report all	Report if: - drug/vaccine related. (Follow ongoing to outcome)	Within 24 hours of learning of event
Pregnancy/ Lactation Exposure	Report if: - participant has been exposed to any protocol-specified intervention (eg, procedure, washout or run-in treatment including placebo run-in) Exception: A positive pregnancy test at the time of initial screening is not a reportable event.	Report all	Previously reported – Follow to completion/termination; report outcome	Within 24 hours of learning of event
ECI (require regulatory reporting)	Report if: - due to intervention - causes exclusion	Report - potential DILI - require regulatory reporting	Not required	Within 24 hours of learning of event
ECI (do not require regulatory reporting)	Report if: - due to intervention - causes exclusion	Report - non-DILI ECIs and those not requiring regulatory reporting	Not required	Within 5 calendar days of learning of event
Cancer	Report if: - due to intervention - causes exclusion	Report all	Not required	Within 5 calendar days of learning of event (unless serious)

Type of Event	Reporting Time Period: Consent to Randomization/ Allocation	Reporting Time Period: Randomization/ Allocation through Protocol-specified Follow-up Period	Reporting Time Period: After the Protocol-specified Follow-up Period	Time Frame to Report Event and Follow-up Information to Sponsor:
Overdose	Report if: - receiving placebo run-in or other run-in medication	Report all	Not required	Within 24 hours of learning of event

DILI=drug-induced liver injury; ECI=event of clinical interest; NSAE=nonserious adverse event; SAE=serious adverse event.

8.4.2 Method of Detecting AEs, SAEs, and Other Reportable Safety Events

Care will be taken not to introduce bias when detecting AEs and/or SAEs and other reportable safety events. Open-ended and nonleading verbal questioning of the participant is the preferred method to inquire about AE occurrence.

8.4.3 Follow-up of AE, SAE, and Other Reportable Safety Event Information

After the initial AE/SAE report, the investigator is required to proactively follow each participant at subsequent visits/contacts. All AEs, SAEs, and other reportable safety events, including pregnancy and exposure during breastfeeding, ECIs, cancer, and overdose will be followed until resolution, stabilization, until the event is otherwise explained, or the participant is lost to follow-up (as defined in Section 7.3). In addition, the investigator will make every attempt to follow all nonserious AEs that occur in randomized participants for outcome. Further information on follow-up procedures is given in Appendix 3.

8.4.4 Regulatory Reporting Requirements for SAE

Prompt notification (within 24 hours) by the investigator to the Sponsor of SAE is essential so that legal obligations and ethical responsibilities towards the safety of participants and the safety of a study intervention under clinical investigation are met.

The Sponsor has a legal responsibility to notify both the local regulatory authority and other regulatory agencies about the safety of a study intervention under clinical investigation. The Sponsor will comply with country-specific regulatory requirements and global laws and regulations relating to safety reporting to regulatory authorities, IRB/IECs, and investigators.

Investigator safety reports must be prepared for SUSARs according to local regulatory requirements and Sponsor policy and forwarded to investigators as necessary.

An investigator who receives an investigator safety report describing an SAE or other specific safety information (eg, summary or listing of SAE) from the Sponsor will file it along with the IB and will notify the IRB/IEC, if appropriate according to local requirements.

8.4.5 Pregnancy and Exposure During Breastfeeding

Information in this section is not applicable since participants are participants capable of producing ejaculate whose partner's pregnancy/lactation information is not required.

8.4.6 Disease-related Events and/or Disease-related Outcomes Not Qualifying as AEs or SAEs

Not applicable.

8.4.7 Events of Clinical Interest

Selected serious and nonserious AEs are also known as ECIs and must be reported to the Sponsor.

Events of clinical interest for this study include:

1. An overdose of Sponsor's product, as defined in Section 8.5.
2. Potential DILI events defined as an elevated AST or ALT laboratory value that is greater than or equal to 3X the ULN and an elevated total bilirubin laboratory value that is greater than or equal to 2X the ULN and, at the same time, an alkaline phosphatase laboratory value that is less than 2X the ULN, as determined by way of protocol-specified laboratory testing or unscheduled laboratory testing.*

*Note: These criteria are based on available regulatory guidance documents. The purpose of the criteria is to specify a threshold of abnormal hepatic tests that may require an additional evaluation for an underlying etiology. The study-site guidance for assessment and follow up of these criteria can be found in the Investigator Study File Binder (or equivalent).

It may also be appropriate to conduct additional evaluation for an underlying etiology in the setting of abnormalities of liver blood tests including AST, ALT, bilirubin, and alkaline phosphatase that do not meet the criteria noted above. In these cases, the decision to proceed with additional evaluation will be made through consultation between the study investigators and the Sponsor Clinical Director. However, abnormalities of liver blood tests that do not meet the criteria noted above are not ECIs for this study.

8.5 Treatment of Overdose

For purposes of this study, an overdose will be defined as any dose of any drug administered as part of the study exceeding the dose prescribed by the protocol. It is up to the investigator or the reporting physician to decide whether a dose is to be considered an overdose, in consultation with the Sponsor.

Sponsor does not recommend specific treatment for an overdose. Decisions regarding dose interruptions or modifications will be made by the investigator in consultation with the Sponsor Clinical Director based on the clinical evaluation of the participant.

8.6 Pharmacokinetics

The decision as to which plasma samples collected will be measured for evaluation of PK or PK-Pharmacodynamics will be collaboratively determined by the Sponsor. If indicated, these samples may also be measured and/or pooled for assay in an exploratory manner for metabolites and/or additional pharmacodynamic markers. Blood samples collected may be stored and further analysis may be performed, if required.

8.6.1 Blood Collection for Plasma MK-2060 and ADA

Sample collection, storage, and shipment instructions for plasma samples will be provided in the Study Operations Manual.

8.7 Pharmacodynamics

Sample collection, storage, and shipment instructions for PD samples (aPTT/PT/FXI activity) will be provided in the Study Operations Manual. They will be performed at a central vendor for PD. The PD data for statistical analysis and potential modeling work will be based on the information from the central vendor for PD. Blood samples collected may be stored and further analysis may be performed, if required.

aPTT and PT at screening, predose, and postdose specified in the SoA will be performed by the central laboratory for safety to monitor safety as defined in Section 8.3.7.

8.8 Biomarkers

Collection of samples for other biomarker research is also part of this study. The following samples for biomarker research will be collected from all participants as specified in the SoA:

- Blood for Genetic Analysis

8.8.1 Planned Genetic Analysis Sample Collection

The planned genetic analysis sample should be drawn for planned analysis of the association between genetic variants in DNA and drug response. This sample will not be collected at the site if there is either a local law or regulation prohibiting collection, or if the IRB/IEC does not approve the collection of the sample for these purposes. If the sample is collected, leftover extracted DNA will be stored for FBR if the participant provides documented informed consent for FBR. If the planned genetic analysis is not approved, but FBR is approved and consent is given, this sample will be collected for the purpose of FBR.

The planned genetic analysis sample should be obtained predose on Day 1 but may be collected at the next scheduled blood draw, if needed. Sample collection, storage, and shipment instructions for planned genetic analysis samples will be in the Operations/Laboratory Manual.

8.9 Future Biomedical Research Sample Collection

If the participant provides documented informed consent for FBR, the following specimens will be obtained as part of FBR:

- Leftover DNA for future research

8.10 Medical Resource Utilization and Health Economics

Medical Resource Utilization and Health Economics are not evaluated in this study.

8.11 Visit Requirements

Visit requirements are outlined in Section 1.3. Specific procedure-related details are provided in Section 8.

8.11.1 Screening

Before intervention randomization, potential participants will be evaluated to determine that they fulfill the entry requirements as set forth in Section 5.

Screening 1 should occur within 28 days prior to intervention randomization. Screening 2 should occur within 5 to 8 days prior to intervention randomization. Screening 2 should occur after review of all data from Screening 1. Dialysis should be done at Screenings 1 and 2.

Participants may be rescreened after consultation with the Sponsor. Rescreening should include all screening procedures (except for blood collection for FSH if a postmenopausal state was confirmed by FSH test) listed in the SoA, including consent review. Rescreen procedures cannot be conducted the day prior to intervention randomization.

8.11.2 Treatment Period

Refer to the SoA (Section 1.3), and Administrative and General Procedures (Section 8.1).

8.11.3 Poststudy

Participants will be required to return to clinic 150 (± 7) days after the dose of study intervention for the poststudy visit.

8.11.4 Phone Call Follow-up

A phone call follow-up or on-site follow-up (dialysis day) will be performed 164 (± 7) days after the dose of study intervention. The follow-up will facilitate the collection of relevant safety information. The participants will be interviewed to obtain information relating to AEs and SAEs since the poststudy clinic visit. All safety information described by the participants must be documented in the source documents and be reviewed by the investigator.

If the follow-up occurs less than 164 days after the dose of study intervention, a subsequent follow-up should be made at 164 (+7) days post the dose of study intervention to determine if any AEs have occurred since 1st follow-up.

If the initial call is unsuccessful, the study site staff should make a total of 3 attempts. All attempts to contact the subjects will be recorded in the source documents.

8.11.5 Critical Procedures Based on Study Objectives: Timing of Procedure

For this study, the blood sample for MK-2060 is the critical procedure.

At any postdose time point, the blood sample for MK-2060 needs to be collected as close to the exact time point as possible. All other procedures should be completed as close to the prescribed/scheduled time as possible. Study procedures can be performed before or after the prescribed/scheduled time.

The order of priority can be changed during the study with joint agreement of the investigator and the Sponsor Clinical Director.

Any nonscheduled procedures required for urgent evaluation of safety concerns take precedence over all routine scheduled procedures.

The following variance in procedure collection times will be permitted.

- Blood collection for PK, PD, ADA, laboratory safety tests, including aPTT/PT, and genetic analysis as outlined in [Table 6](#).

Table 6 Blood Collection Windows

Collection Time	Collection Window
Predose	Within 3 hrs prior to the initiation of dialysis
1 hr	Immediately prior to the end of IV infusion (i.e. no more than 5 min before anticipated time of the end of IV infusion)
12 hrs	±15 min
24 hrs	±1 hr
48 hrs	± 1 hr and prior to the initiation of dialysis
52 hrs	Post dialysis
96 hrs	± 2 hrs and prior to the initiation of dialysis. If this prescribed time is not dialysis day, +1 day and prior to the initiation of dialysis.
168 hrs	± 2 hrs and prior to the initiation of dialysis. Blood samples for PK and PD will be also collected at post dialysis.
Day 12	±1 day and within 12 hrs prior to the initiation of dialysis
Days 15 and 22	±2 days and within 12 hrs prior to the initiation of dialysis
Day 29	±3 days and within 12 hrs prior to the initiation of dialysis. Blood samples for PK and PD will be also collected at post dialysis.
Days 60 and 90	±5 days and within 12 hrs prior to the initiation of dialysis
Day 120	±7 days and within 12 hrs prior to the initiation of dialysis. Blood samples for PK and PD will be also collected at post dialysis.
Day 150	±7 days and within 12 hrs prior to the initiation of dialysis

- Safety evaluations for PE, systemic infusion reaction assessment, VS and 12-lead ECG as outlined in [Table 7](#).

Table 7 Safety Evaluations Windows

Evaluation Time	Evaluation Window
Predose	Within 3 hrs prior to the initiation of dialysis
15 and 30 min	±15 min
1 and 2 hrs	
3.5 hrs	±15 min
8 hrs	±15 min
12 hrs	±30 min
24 hrs	±1 hr
48 hrs	± 2 hrs and prior to the initiation of dialysis
96 hrs	± 2 hrs and prior to the initiation of dialysis. If this prescribed time is not dialysis day, +1 day and prior to the initiation of dialysis.
168 hrs	± 2 hrs and prior to the initiation of dialysis
Day 12	±1 day and within 12 hrs prior to the initiation of dialysis
Days 15 and 22	±2 days and within 12 hrs prior to the initiation of dialysis
Day 29	±3 days and within 12 hrs prior to the initiation of dialysis
Days 60 and 90	±5 days and within 12 hrs prior to the initiation of dialysis
Days 120 and 150	±7 days and within 12 hrs prior to the initiation of dialysis

- Assessment of time to adequate hemostasis: After dialysis catheters are removed from the dialysis access site.
- Hemoccult Test: within 2 days of specified timepoint.

8.11.6 Study Design/Dosing/Procedures Modifications Permitted Within Protocol Parameters

This is a Phase 1 assessment of MK-2060 in humans, and the PK, pharmacodynamic, and safety profiles of the compound are still being elucidated. This protocol is written with some flexibility to accommodate the inherent dynamic nature of Phase 1 clinical studies.

Modifications to the dose, dosing regimen, and/or clinical or laboratory procedures currently outlined may be required to achieve the scientific goals of the study objectives and/or to ensure appropriate safety monitoring of the study participants.

As such, some alterations from the currently outlined dose and/or dosing regimen may be permitted based on newly available data, but the maximum daily dose may not exceed those currently outlined in the protocol.

- Addition of PK pause
- Instructions to take study intervention with or without food or drink may be modified based on newly available data

- Modification of the PK/pharmacodynamic sample processing and shipping details based on newly available data

The PK/pharmacodynamic sampling scheme currently outlined in the protocol may be modified during the study based on newly available PK or pharmacodynamic data (eg, to obtain data closer to the time of peak plasma concentrations). If indicated, these collected samples may also be assayed in an exploratory manner for metabolites and/or additional pharmacodynamic markers.

Up to additional 50 mL of blood may be drawn for safety, PK, and/or pharmacodynamic analyses. The total blood volume withdrawn from any single participant will not exceed the maximum allowable volume during his/her participation in the entire study (Appendix 8).

The timing of procedures for assessment of safety procedures (eg, vital signs, ECG, safety laboratory tests, etc) may be modified during the study based on newly available data. Additional laboratory safety tests may be added to blood samples previously drawn to obtain additional safety information. These changes will not increase the number of study procedures for a given participant during his/her participation in the entire study.

It is understood that the current study may use some or none of the alterations described above. Any alteration made to this protocol to meet the study objectives must be detailed by the Sponsor in a letter to the Study File and forwarded to the investigator for retention. The letter may be forwarded to the IRB/IEC at the discretion of the investigator.

9 STATISTICAL ANALYSIS PLAN

9.1 Statistical Analysis Plan Summary

This section contains a summary of the statistical analyses for this trial. Full detail can be found in the subsequent sections.

Safety

AEs will be tabulated by treatment group. Summary statistics and plots will be generated for raw laboratory safety tests, ECGs, and vital sign as well as for change from baseline, as deemed clinically appropriate. Depending on the safety parameter, the difference from baseline will either be computed on the original scale (raw change from baseline) or on the log scale and back-transformed for reporting (percent change from baseline).

Pharmacokinetics

Individual values will be listed for each PK parameter and appropriate non-model based descriptive statistics will be provided: N (number of participants with non-missing data), arithmetic mean, standard deviation, arithmetic percent CV (calculated as $100 \times$ standard deviation/ arithmetic mean), median, minimum, maximum, geometric mean and geometric percent CV (calculated as $100 \times \text{sqrt}(\text{exp}(s^2)-1)$, where s^2 is the observed variance on the natural log-scale).

Pharmacodynamics

Individual aPTT fold-change from baseline values will be natural log-transformed and evaluated with a linear mixed effect model containing fixed effects for treatment, time and treatment by time interaction and random effect for participant. Least squares means and 95% confidence intervals for each treatment, and for the between-treatment difference (MK-2060-placebo) and 90% CI at each dose level, will be obtained by time. These estimates will be back-transformed to obtain GM aPTT fold-change from baseline by treatment time and the GMR (MK-2060 fold-change from baseline/placebo fold-change from baseline) by dose and time.

The proportion of participants with a fold-increase in aPTT 168 hours after a single dose of at least 1.5 will be tabulated.

Sample Size and Power Calculations

The total participants of approximately 16 (MK-2060=approximately ~~CC~~ placebo=approximately ~~CC~~) is considered to be adequate to address the primary objective of the study.

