4.2.2 Rationale for the Use of Placebo

The primary goal of the study is to evaluate the safety and tolerability of MK-2060 in Japanese older participants with ESRD on dialysis. A placebo-controlled study will allow for an unbiased assessment of safety and tolerability of MK-2060. Secondary and exploratory outcomes are also supported by the use of placebo, including evaluation of the effect of MK-

2060 on aPTT following single IV dose, which should only be observed in participants with active treatment.

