16. Participated in another investigational study within 1 month (or 5 half-lives, whichever is greater) prior to Screening 1. The window will be derived from the date of the last visit in the previous study.

Diagnostic Assessments

17. Has a BP > 190 mmHg systolic or > 110 mmHg diastolic obtained at Screening 2 or predose.
18. Has blood coagulation test (aPTT or PT) above 1.2X ULN at Screening 1 (confirmed by recheck) from the central laboratory for safety.
19. Has ALT or AST above 1.5X ULN at Screening 1 or 2 which are considered clinically significant by the investigator from the central laboratory for safety.
20. Exclusion criteria for ECG performed at Screening 1 or predose:
 - HR < 40 or > 110 bpm
 - QTc interval > 500 msec
 - Any significant arrhythmia or conduction abnormality, (including but not specific to atrioventricular block [2nd degree or higher], Wolff Parkinson White syndrome [unless curative radio ablation therapy]), which, in the opinion of the investigator and Sponsor, could interfere with the safety for the individual patient.
 - Non-sustained or sustained ventricular tachycardia (greater than 2 consecutive ventricular ectopic beats at a rate of greater than 1.7/second).

Other Exclusions

21. Consumes greater than 3 servings of alcoholic beverages (1 serving is approximately equivalent to: beer [354 mL], wine [118 mL], or distilled spirits [29.5 mL]) per day. Participants who consume 4 servings of alcoholic beverages per day may be enrolled at the discretion of the investigator.
22. Consumes excessive amounts, defined as greater than 6 servings (1 serving is approximately equivalent to 120 mg of caffeine) of coffee, tea, cola, energy drinks, or other caffeinated beverages per day.
23. A regular user of cannabis, any illicit drugs or has a history of drug (including alcohol) abuse within approximately 2 years. Participants must have a negative saliva drug screen at Screening 1. Participants with a positive drug screen due to the use of physician prescribed medications may be enrolled at the discretion of the investigator.

24. The investigator has any concern regarding safe participation in the study or for any other reason the investigator considers the participant inappropriate for participation in the study.
25. Is or has an immediate family member (eg, spouse, parent/legal guardian, sibling, or child) who is investigational site or Sponsor staff directly involved with this study.

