6.3.2 Stratification

No stratification based on age, sex, or other characteristics will be used in this study.

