6.6.1 Stopping Rules

The following stopping rules will be used during the conduct of this study.

If any of the below stopping rules are met, the study will be paused, and no further dosing will occur until the Sponsor has reviewed the totality of data available. The study can be restarted based on joint agreement with the Sponsor and investigator. If needed, a substantial amendment may be submitted for approval.

1. An individual participant reports an SAE considered related to the study intervention by the investigator.
2. Two (2) or more participants (at the same dose level) report Severe Nonserious AEs considered related to the study intervention by the investigator.
3. If one or more infusion AEs of severe intensity considered related to the study intervention by the investigator occurs in 2 or more participants.
4. An increase aPTT > 4.0 -fold versus baseline as confirmed after repeat measurement in 2 or more participants. aPTT values from the central laboratory for safety will be used for this rule and aPTT measured at the Screening Visit should be used as baseline value.
5. An increase PT > 1.5 -fold versus baseline as confirmed after repeat measurement in 2 or more participants. PT values from the central laboratory for safety will be used for this rule and PT measured at the Screening Visit should be used as baseline value.

Participants who receive intradialytic heparin will likely have an increased aPTT at the 1-hour timepoint post dosing due to the pharmacologic effects of heparin. In order to allow for the evaluation of the pharmacologic effects of MK-2060 alone, the 12-hour post-dose aPTT will be the first timepoint used to assess aPTT stopping criteria for participants who receive intradialytic heparin. Heparin dosed at the time of dialysis should not interfere with aPTT at this 12-hour post-dose timepoint (heparin t_{1/2} is ~1hr). All other aPTT at safety labs throughout the course of the study will be drawn pre-dialysis and in the absence of heparin.

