These criterion for aPTT (> 4.0 -fold in 2 or more participants) was based upon that aPTT prolongations greater than 3-fold have been observed in severe FXI-deficient populations [Asakai, R., et al 1991]. Using the same aPTT assay which was used by the central laboratory for PD in this study, samples of pooled normal human plasma were compared to those from FXI-deficient patients, which were tested individually [Ellsworth K 2018]. In normal human plasma, the clot time ranged between 31.8 and 36.4 seconds. In plasma from FXI deficient patients, the clot time ranged between 99.5 and 128.1 seconds, which corresponded to a range of 2.9 to 3.9-fold prolongation in aPTT compared to that of the normal human plasma. From data collected in MK-2060-001, it appears that higher doses of

MK-2060 provide similar inhibition as the severe FXI-deficient phenotype, evidenced by MK-2060-associated increases in aPTT (local lab) up to 3.9-fold at the highest dose in MK-2060-001 (120 mg administered subcutaneously). These aPTT prolongations occurred in the absence of prolongation of PT and were associated with >95% inhibition of FXI activity, with no evidence of MK-2060-related AE. Therefore, the stopping criterion based upon an aPTT is >4-fold after repeat measurement in 2 or more participants.

The safety of participants will be assessed on an ongoing basis, and while conditions that could warrant stopping dosing are not limited to those noted above, these criteria are meant to pre-specify circumstances under which the study may be stopped to review the available safety data. Importantly, if any criterion listed above occurs, further dosing will be stopped and review of available safety data by the investigator and Sponsor will be required prior to continuing the study, which might include modification of safety monitoring procedures.

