9.4 Analysis Endpoints

Primary Endpoints

1. AEs

Secondary Endpoints

1. Pharmacokinetics: Plasma AUC0-inf, AUC0-last, AUC0-168, Cmax, C168, Tmax, Tlast, t1/2, CL and Vz
2. Pharmacodynamics: aPTT (fold change from baseline)

Exploratory Endpoints

1. Factor XI activity (fold change from baseline)
2. Prothrombin time (fold change from baseline)
3. Time to hemostasis

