4. ADA

For change from baseline, the baseline is defined as the panel-specific pre-dose value.

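### The aPTT fold-change model omits predose aPTT as a covariate, so in about 16 unstratified participants a chance baseline difference can leave a small error in the MK-2060/placebo ratio

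*Combined protocol and SAP*

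**What the plan says.** The secondary pharmacodynamic endpoint in section 9.4 is aPTT as fold change from baseline, and "For change from baseline, the baseline is defined as the panel-specific pre-dose value". Sections 9.1 and 9.6 give the same analysis: log-transformed fold-changes in a linear mixed model "containing fixed effects for treatment, time and treatment by time interaction and random effect for participant". The outputs are geometric mean fold-changes by treatment and time, and the MK-2060/placebo GMR at each time with a 90% CI. No section adds a baseline covariate.

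On allocation, section 6.3.2 says "No stratification based on age, sex, or other characteristics will be used in this study". About 16 participants are planned (section 9.9); the arm sizes are redacted. Section 9.8 confirms that there are no prespecified hypotheses, so the analysis is estimation only.

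**The concern.** Using fold-change as the response does not adjust for baseline in general. It subtracts the whole of log baseline, which is the right amount only if participants who start higher stay proportionally higher afterwards, that is, if the slope of log postdose on log predose is 1. Assay and day-to-day variation in the predose value usually pull that slope below 1. The fold-change then over-corrects, and the arm that starts higher by chance shows too small a fold-change.

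Only one predose PD sample is planned. Its error therefore enters every postdose fold-change, and averaging over visits does not remove it. The random participant effect does not remove it either, because it does not adjust the treatment contrast for baseline.

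At stake is the accuracy, for the one allocation that occurs, of the only model-based result for this endpoint. The tabulation of 168-hour responders and the aPTT stopping rule do not use this model.

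**Working it through.** The documents state no SD, slope or precision for aPTT, so there is no figure of the plan's own to reproduce. Baseline log SD, slopes and arm sizes below are assumptions, shown over a range.

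**Number of PD samples.** From Table 6 in section 8.11.5 and the schedule of activities, the postdose draws are 1, 12, 24, 48, 52 and 96 h (6), 168 h twice (2), Days 12, 15 and 22 (3), Day 29 twice (2), Days 60 and 90 (2), Day 120 twice (2) and Day 150 (1). That is 18. With 1 predose draw the total is 19, which matches Appendix 8.

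**Conditional error, equal slopes.** Let b be the true slope in both arms and D the difference in mean log baseline (MK-2060 minus placebo).
- Error in log GMR = (b − 1) × D.
- SD of D = s × √(1/n₁ + 1/n₂), where s is the baseline log SD. The multiplier is 0.500 for 8:8 and 0.577 for 12:4.
- Size of the GMR shift at an m-SD imbalance = exp[(1 − b) × m × multiplier × s].

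| Baseline log SD | Smallest shift (8:8, b = 0.9) | Largest shift (12:4, b = 0.5) |
|---|---|---|
| 0.08–0.16, m = 1 | exp(0.1 × 0.500 × 0.08) = 1.0040 | exp(0.5 × 0.577 × 0.16) = 1.0473 |
| 0.08–0.16, m = 2 | 1.0080 | 1.0968 |
| 0.08 only, m = 1 | 1.0040 | 1.0234 |
| 0.08 only, m = 2 | 1.0080 | 1.0473 |

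**Where in the range.** Section 5.2 excludes a participant who "Has blood coagulation test (aPTT or PT) above 1.2X ULN at Screening 1", and section 6.6.1 reports that "In normal human plasma, the clot time ranged between 31.8 and 36.4 seconds". If that range stands in for the reference range, the limit is 1.2 × 36.4 = 43.68 s. If 31.8 to 43.68 s spans ±2 SD, the log SD is ln(43.68/31.8)/4 = 0.317/4 = 0.079. This is a rough guide: the range comes from pooled plasma in the PD assay, whereas the limit applies to the safety laboratory.

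**Does the random participant effect help?** In a simulated balanced data set, the planned mixed-model contrast equalled the raw difference in arm means of log fold-change (0.7373 both ways). Adding baseline changed it to 0.708. In 20,000 simulated single-visit trials (12:4, log SD 0.12, slope 0.5), the error changed by −0.51 per unit of D as planned and by about 0 with the covariate. The SD of the log GMR estimate fell from 0.069 to 0.062.

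**Interval coverage.** The simulation used 18 samples, a random participant effect, participant and residual SDs of 0.7 times the baseline SD each, and 40,000 trials per case. With equal slopes, 90% CI coverage was about 90% overall and at a 1-SD imbalance. At a 2-SD imbalance (|z| 1.75–2.25, about 2,200 trials per case) it was:

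| Slopes (MK-2060/placebo) | Allocation | As planned | With covariate |
|---|---|---|---|
| 0.5/0.5 | 8:8 | 81.3% | 91.0% |
| 0.5/0.5 | 12:4 | 80.4% | 90.6% |
| 0.7/0.7 | 8:8 | 86.8% | 90.5% |
| 0.7/0.7 | 12:4 | 85.9% | 89.2% |
| 0.9/0.9 | 8:8 | 88.7% | 89.3% |
| 0.9/0.9 | 12:4 | 90.1% | 91.0% |
| 0.5/0.9 | 12:4 | 90.3% | 86.4% |
| 0.9/0.5 | 12:4 | 79.8% | 85.9% |

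**Unequal slopes.** With slopes bT and bP, arm sizes nT and nP, and N = nT + nP, the error as a multiple of D is:
- planned: (bT − 1)nP/N + (bP − 1)nT/N;
- common slope: bT·nP/N + bP·nT/N − [bT(nT − 1) + bP(nP − 1)]/(N − 2).

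For 12:4 with slopes 0.5/0.9, the planned value is −0.5 × 0.25 − 0.1 × 0.75 = −0.200. The common-slope value is 0.800 − (5.5 + 2.7)/14 = +0.214. For 0.3/0.9 the pair is −0.250 then +0.321, and for 0.9/0.5 it is −0.400 then −0.214. For 10:6 with 0.5/0.9 it is −0.250 then +0.107. For 8:8 the common slope gives 0 for any pair; with 0.5/0.9 the planned value is −0.300.

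**Slope differing by visit.** The predose sample is drawn before dialysis and the 1-hour sample during it. Section 6.6.1 warns that "Participants who receive intradialytic heparin will likely have an increased aPTT at the 1-hour timepoint post dosing". If the slope were 0.3 at 1 hour and 0.7 elsewhere, the common slope would average (0.3 + 17 × 0.7)/18 = 0.678. The 1-hour multiple would go from −0.70 to −0.38, and the others from −0.30 to +0.02.

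**The case against.** The strongest reply is that nothing is wrong with the plan. The estimator is unbiased over randomisation, with equal slopes its interval already allows for chance imbalance, and it estimates the endpoint as defined. No hypothesis test depends on it. At a log SD of 0.08 a 1-SD imbalance moves the GMR by at most 2.3%, about a quarter of a single-visit 90% CI half-width of 7–9% under the simulation's inputs. Coverage near 80% with equal slopes needs both a slope of 0.5 and a roughly 2-SD imbalance, which occurs in about 5–6% of trials (2,200/40,000). With participant and residual SDs doubled, the gap at slope 0.5 shrinks to 86–87.5% as planned against 89–91% adjusted. All of this stands, and it is why the point is optional.

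The more serious objection is that the remedy can do harm. Section 4.2.2 expects an aPTT effect "which should only be observed in participants with active treatment", so slopes may differ by arm. If the MK-2060 slope is the lower one and allocation is 12:4, the common-slope model reverses the error and can enlarge it. This also stands, and whether it applies depends on the redacted ratio. It is a reason to report both models and inspect the slopes, but not to leave baseline out: at 8:8 the concern disappears, and in the 10:6 and 12:4 (0.9/0.5) examples the covariate reduces the error.

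A last reply is that the term could be added later. Section 9.2 would then require it to be listed and explained as a deviation, and it would look data-driven.

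**Conclusion.** The point holds as a low-priority improvement, with medium confidence. The model fixes the baseline slope at 1, and the resulting error is conditional on the allocation that occurs. Over the assumed inputs (equal slopes 0.5–0.9, baseline log SD 0.08–0.16, 8:8 to 12:4) it is 0.4–4.7% of the GMR at a 1-SD imbalance and 0.8–9.7% at 2 SD. At the SD suggested by the eligibility limit it is 0.4–2.3% and 0.8–4.7%. If the true slope is about 0.9 or higher, there is little or nothing to gain. The benefit of the covariate depends on similar slopes in the two arms or equal allocation, and neither can be confirmed from the public documents.

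**What to change.** In sections 9.1 and 9.6, add log predose aPTT from the PD laboratory as a fixed effect with one common slope, and report least squares means and GMRs at the overall mean log baseline. Keep the current model as a sensitivity analysis and report both. Prespecify a baseline-by-time term as a secondary check only, mainly for the 1-hour on-dialysis sample, which a common slope does not fully correct. If allocation is unequal, also plot log postdose against log predose by arm, because the adjusted result then relies on similar slopes.

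The text change is one line in each section and needs no new samples, although the second model, the check and the plot add some reporting. In precision, the 18-sample model's 90% CI is about 2% wider if the true slope is 1 (ratio 1.023). It is narrower at slope 0.7 (0.977) and 0.5 (0.909). For a single visit at slope 1 the ratio is √(13/12) × 1.7709/1.7613 = 1.047. The remaining risk is unequal slopes with unequal allocation, where the adjusted estimate can be no better or worse.
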